5.2 EXCLUSION CRITERIA

Participants are excluded from the study if any of the following criteria apply:

Medical conditions

- E 01. Clinically significant medical history or ongoing chronic illness that would jeopardize the safety of the participant or compromise the quality of the data derived from his/her participation in the study.
- E 02. Clinically relevant infection within the month prior to enrollment.
- E 03. History of venous or arterial thrombosis within the year prior to enrollment.
- E 04. Clinical diagnosis of SLE.

- E 05. Secondary ITP from any cause including lymphoma, chronic lymphocytic leukemia, and drug-induced thrombocytopenia.
- E 06. Positive hepatitis B surface antigen (HBsAg) or active HCV infection. For patients with an isolated positive anti-HBc antibody, hepatitis B virus (HBV) DNA by polymerase chain reaction (PCR) must be negative at Screening. Patients who have undergone hepatitis C antiviral therapy may be enrolled if they are documented to be HCV RNA negative on at least 2 occasions separated by at least 3 months (including 1 RNA test at least 6 months after completion of antiviral therapy) and are also HCV RNA negative at Screening.
- E 07. HIV infection.
- E 08. Positive SARS-CoV-2 molecular test (if coronavirus disease [COVID-19] testing required).
Note: Participants switching from sutmilimab may be enrolled even with a positive SARS-CoV-2 test, as per the judgement of the Investigator.
- E 09. Pregnant or lactating women.
- E 10. Eastern Cooperative Oncology Group (ECOG) performance status >2.
- E 11. Sensitivity to any of the study interventions, or components thereof, or other allergy that, in the opinion of the Investigator, compromises participation in the study.

Prior/concomitant therapy

- E 12. Use of aspirin, nonsteroidal anti-inflammatory drugs (NSAIDS), or anticoagulants within 1 week prior to enrollment.

Prior/concurrent clinical study experience

- E 13. Concurrent treatment with other experimental drugs or participation in another clinical trial with any investigational drug (with the exclusion of sutmilimab) within 30 days or 5 half-lives, whichever is greater, prior to enrollment.

Diagnostic assessments

- E 14. Hemoglobin level <10 g/dL.
- E 15. White blood cells (WBCs) or neutrophil counts outside of normal limits, if considered clinically significant by the Investigator. Elevated WBC/absolute neutrophil count (ANC) attributed to steroid treatment is acceptable.
- E 16. Prothrombin time/international normalized ratio (PT/INR) or activated partial thromboplastin time (aPTT) outside of the normal limits, if considered clinically significant by the Investigator.

Other exclusions

- E 17. Individuals accommodated in an institution because of regulatory or legal order; prisoners or participants who are legally institutionalized.
- E 18. Participants not suitable for participation, whatever the reason, as judged by the Investigator, including medical or clinical conditions, or participants potentially at risk of noncompliance to study procedures.
- E 19. Participants who are employees of the clinical study site or other individuals directly involved in the conduct of the study, or immediate family members of such individuals (in conjunction with Section 1.61 of the International Council for Harmonisation - Good Clinical Practice (ICH-GCP Ordinance E6).
- E 20. Any specific situation during study implementation/course that may raise ethics considerations.

5.3 LIFESTYLE CONSIDERATIONS

Not applicable.

5.4 SCREEN FAILURES

Screen failures are defined as participants who consent to participate in the clinical study but are not subsequently enrolled. A minimal set of screen failure information is required to ensure transparent reporting of screen failure participants to meet the Consolidated Standards of Reporting Trials (CONSORT) publishing requirements and to respond to queries from regulatory authorities. Minimal information includes demography, screen failure reasons, eligibility criteria, and any serious adverse event (SAE).

Individuals who do not meet the criteria for participation in this study (screen failures) may be rescreened.

5.5 CRITERIA FOR TEMPORARILY DELAYING ENROLLMENT/STUDY INTERVENTION ADMINISTRATION

During a regional or national emergency declared by a governmental agency, if the site is unable to adequately follow protocol mandated procedures, contingency measures are proposed in Appendix 9 ([Section 10.9](#)) and should be considered for screening/enrollment/administration of study intervention.

6 STUDY INTERVENTION(S) AND CONCOMITANT THERAPY

Study intervention is defined as any investigational intervention(s), marketed product(s), placebo, or medical device(s) intended to be administered to a study participant according to the study protocol.

6.1 STUDY INTERVENTION(S) ADMINISTERED

Table 3 - Overview of study interventions administered

Intervention label	BIVV020
Intervention name	BIVV020, humanized anti-C1s monoclonal antibody
Type	Drug
Dose formulation	BIVV020 supplied in single use vials containing 750 mg (150 mg/mL; extractable volume of 5 mL)
Unit dose strength(s)	750 mg/5 mL
Dosage level(s)	50 mg/kg IV loading dose, followed by 600 mg SC weekly
Route of administration	IV loading dose; SC maintenance administration
Use	Experimental
IMP or NIMP	IMP
Packaging and labeling	Details are provided in the Pharmacy Manual.
Current/Former name(s) or alias(es)	Not Applicable

Table 4 - Arms and associated interventions

Arm name	BIVV020
Associated interventions (intervention label[s])	Details are provided in the Pharmacy Manual

An intravenous (IV) loading dose of BIVV020 at 50 mg/kg will be administered on Day 1, and will be followed by maintenance doses of 600 mg SC weekly starting on Day 8. For the first 5 weeks of maintenance therapy, the injections will be performed by the site staff, and participants will receive education on self-administration. At Week 6, the participant (or their caregiver) will perform the injection under the supervision of the site staff. Starting at Week 7, the injections will be performed by the participants or caregiver at home. See [Section 4.1](#) for additional details regarding the locations for IMP administration over the course of the study.

6.1.1 Intravenous loading dose administration

- The loading dose of BIVV020 at 50 mg/kg IV will be administered on Day 1.
- Infusion of the BIVV020 IV preparation should be done using a large volume infusion pump.

- Approximately 50 mL of dosing solution and approximately 60 mL of flush will be administered. An infusion pump will be programmed to deliver 90 mL at a rate of 150 mL/hr. Any excess volume over 90 mL will remain in-line to account for IV dead space. The total time for infusion will be approximately 45 minutes.
- The total time of dose preparation (vial puncture) to completion of administration may not exceed 4 hours.
- Participants will remain in the clinic for at least 4 hours after the start of IMP administration.
- The administration process is to be documented in the source document worksheet or within the administration/dosing logs.

Further details can be found in the Pharmacy Manual.

6.1.2 Subcutaneous dose administration

- The 600 mg SC dose will be administered in 2 injections; each injection will be 2 mL.
- Depending the study visit, SC administration may be performed at the site or by the patient/caregiver at home. In case of home administration, a Patient Diary should be used to record administration details.
- The recommended injection sites include:
 - Abdomen (except for the 2 inch [\sim 5 cm] radius area around the navel). This is the preferred location.
 - Top of thighs.
 - Outer area of upper arm (by caregivers only).
- The SC injections should be given consecutively, but may be spaced apart by up to 30 minutes. A different site for each injection should be used (eg different locations on the abdomen).
- The total time of dose preparation (vial puncture) to completion of administration may not exceed 4 hours.
- Participants should be observed for 30 minutes after IMP administration for the first 6 SC administrations.

Further details can be found in the Pharmacy Manual.

BIVV020 may be supplied at the site or from the Principal Investigator/site/Sponsor to the participant via a Sponsor-approved courier company (direct-to-patient [DTP]) where allowed by local regulations and agreed upon by the participant. The participant/Investigator can refuse this option. Details are provided in the Pharmacy Manual.

For a regional or national emergency declared by a governmental agency that results in travel restrictions, confinement, or restricted site access, contingency measures are included in Appendix 9 ([Section 10.9](#)).

A complete description of BIVV020 and its proper handling will be provided in the Pharmacy Manual available to the clinical site. The appropriate number of kits will be dispensed as necessary for the periods between visits (please refer to SoA [Section 1.3](#)). Storage conditions and use-by-end date (when required by country regulations) are part of the label text.

6.2 PREPARATION/HANDLING/STORAGE/ACCOUNTABILITY

1. The Investigator or designee must confirm appropriate temperature conditions have been maintained during transit for all study intervention received. Any discrepancies must be reported and resolved before use of the study intervention.
2. Only participants enrolled in the study may receive study intervention and only authorized site staff may administer it at clinic visits. All study intervention stored at the sites must be stored in a secure, environmentally controlled, and monitored (manual or automated) area in accordance with the labeled storage conditions with access limited to the Investigator and authorized site staff.
3. The Investigator, institution, or the head of the medical institution (where applicable) is responsible for study intervention accountability, reconciliation, and record maintenance (ie, receipt, reconciliation, and final disposition records).

Any quality issue noticed with the receipt or use of an IMP (deficiency in condition, appearance, pertaining documentation, labeling, expiration date, etc) must be promptly notified to the Sponsor. Some deficiencies may be recorded through a complaint procedure (see [Section 8.3.7](#)).

A potential defect in the quality of IMP may be subject to initiation of a recall procedure by the Sponsor. In this case, the Investigator will be responsible for promptly addressing any request made by the Sponsor, in order to recall the IMP and eliminate potential hazards.

Under no circumstances will the Investigator supply IMP to a third party (except for DTP shipment, for which a courier company has been approved by the Sponsor), allow the IMP to be used other than as directed by this clinical trial protocol, or dispose of IMP in any other manner.

Additional information regarding treatment allocation, preparation and dispensation are available in the Pharmacy Manual.

6.3 MEASURES TO MINIMIZE BIAS: RANDOMIZATION AND BLINDING

Not applicable.

6.4 STUDY INTERVENTION COMPLIANCE

- IMP accountability:
 - Intervention units are returned by the participant at each visit. In case of DTP process, the intervention units can be returned by the carrier (if defined in the contract).

- The Investigator counts the number of vials, etc, remaining in the returned packs, and fills in the Intervention Log Form.
- The Investigator records the dosing information on the appropriate page(s) of the case report form (CRF).
- The monitor in charge of the study then checks the CRF data by comparing them with the IMP which he/she has retrieved and intervention log forms.

Starting at Week 7, the injections will be performed by the patient or caregiver, either at home or in the clinic at scheduled visits. When participants self-administer the study intervention at home, they will be provided with a paper diary or e-diary to record their administrations.

The date and time of each dose administered in the clinic will be recorded in the source documents and recorded. The dose of study intervention and study participant identification will be confirmed at the time of dosing by a member of the study site staff other than the person administering the study intervention. Deviation(s) from the prescribed dosage regimen should be recorded.

A record of the quantity of BIVV020 units dispensed to and administered by each participant must be maintained and reconciled with study intervention and compliance records. Intervention start and stop dates, including dates for intervention delays and/or dose reductions will also be recorded.

6.5 DOSE MODIFICATION

Not applicable.

6.6 CONTINUED ACCESS TO INTERVENTION AFTER THE END OF THE STUDY

Participants will continue to receive BIVV020 until the last participant enrolled has completed 52 weeks of treatment. After that time, a long-term extension study may be available for participants to continue to receive BIVV020. If a long-term extension study is available, the follow up period for this study may not be applicable or may be modified as per the long-term extension study.

6.7 TREATMENT OF OVERDOSE

The Sponsor does not recommend specific treatment for an overdose, as there is no specific antidote. However, any supportive medical treatment may be administered, based on evaluation and clinical findings.

In the event of an overdose, the Investigator should:

1. Contact the Sponsor immediately.
2. Evaluate the participant to determine, in consultation with the Sponsor, whether study intervention should be interrupted or whether the dose should be reduced.

3. Obtain a plasma sample for PK analysis within 7 days from the date of the last dose of study intervention if requested by the Sponsor (determined on a case-by-case basis).
4. Document appropriately in the CRF.

6.8 CONCOMITANT THERAPY

Any medication or vaccine (including over the counter or prescription medicines, vitamins, and/or herbal supplements, and rescue medication) that the participant is receiving at the time of enrollment or receives during the study must be recorded along with:

- Reason for use
- Dates of administration including start and end dates
- Dosage information including dose and frequency

Vaccinations such as seasonal influenza vaccines and other recommended vaccines and booster vaccinations are permitted as per local standard of care, investigator discretion, and local labels.

Concurrent administration of ITP medications (corticosteroids, IVIg, azathioprine, danazol, cyclosporine A, mycophenolate mofetil, or thrombopoietin receptor agonists) is acceptable provided the patient has been on a stable dose for at least 1 month. This applies for both new patients and patients who were previously receiving sutimlimab in Study TDR16218.

Corticosteroids, thrombopoietin receptor agonists, and IVIg are permitted, if the following requirements are met:

- A) Corticosteroids: the first dose of BIVV020 may be dosed only ≥ 4 days after a steroid pulse (single dose of >0.5 mg/kg prednisone equivalent or an increase in prednisone equivalent dose from prior levels) for acute ITP treatment
- B) Thrombopoietin receptor agonists: If receiving weekly thrombopoietin receptor agonist dosing, the last dose must have been administered ≥ 7 days before the first dose of BIVV020. If receiving daily thrombopoietin receptor agonist dosing, the last dose must have been administered ≥ 24 hours before the first dose of BIVV020. Thrombopoietin receptor agonists may be restarted by the Investigator if a participant has an insufficient response to BIVV020.
- C) Intravenous Ig (IVIg): the first dose of BIVV020 must be dosed ≥ 1 day after a dose of IVIg. A single dose of IVIg is allowed during the study; additional doses after the first dose must be approved by the Sponsor.

The Medical Monitor should be contacted if there are any questions regarding concomitant or prior therapy.

6.8.1 Rescue medicine

Rescue medicines given for acute episodes of thrombocytopenia/bleeding, such as steroid pulse/bolus, thrombopoietin receptor agonists, or platelet transfusion are allowed (see above for guidance on IVIg). Additionally, increasing the dose of concomitant ITP medications to prevent or treat bleeding due to low platelet counts is allowed and would be considered rescue therapy.

7 DISCONTINUATION OF STUDY INTERVENTION AND PARTICIPANT DISCONTINUATION/WITHDRAWAL

7.1 DISCONTINUATION OF STUDY INTERVENTION

7.1.1 Permanent discontinuation

In rare instances, it may be necessary for a participant to permanently/definitely discontinue the study intervention. If this occurs, a new participant may be enrolled to replace the one who was discontinued, unless the permanent discontinuation was due to a BIVV020-related adverse reaction or safety concern.

The Investigator/Sponsor must permanently discontinue dosing with BIVV020 in a participant if any of the following participant-level stopping rules are met:

- Pregnancy in a participant while receiving study drug.
- Change in compliance with inclusion/exclusion criteria that is clinically relevant and affects patient's safety.
- Intake of non-permitted concomitant medications that might affect participant's safety or study assessments/objectives.
- An allergic reaction, including an anaphylactic reaction, in association with BIVV020 administration.
- SLE or any other immune complex disease.
- Meningococcal infection.
- Occurrence of AEs that, in the opinion of Investigator/Sponsor, may jeopardize patient safety or data integrity. These include, but are not limited to, abnormal liver tests and abnormal QTc, meeting the stopping criteria (see [Section 7.1.2](#), [Section 7.1.3](#), [Appendix 6](#), [Section 10.6](#)).
- Lack of efficacy (see [Section 7.1.4](#)).
- Participant misses more than 3 consecutive doses of BIVV020 without Investigator approval. If a participant misses 3 consecutive doses and the Investigator believes the participant should remain in the study, a protocol for BIVV020 re-initiation may be considered, in consultation with the Sponsor.

Handling of participants after permanent intervention discontinuation

If study intervention is definitively discontinued, the participant should continue to be followed for an additional 22 weeks. The procedures listed for the EOS visit as per the SoA should be performed at the final visit.

All cases of definitive intervention discontinuation must be recorded by the Investigator in the appropriate pages of the electronic case report form (eCRF) when considered as confirmed.

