4 STUDY DESIGN

4.1 OVERALL DESIGN

- This is a Phase 2a open-label, non-randomized, international, multicenter study to evaluate the efficacy, safety, and tolerability of BIVV020 in adults with persistent/chronic primary ITP.
- The study will enroll approximately 12 participants: up to 6 participants who have previously received and responded to sutimlimab (BIVV009) in study TDR16218, as well as participants who have not previously received sutimlimab.
- The Screening Period will be up to 56 days. Screening begins from the time of the signing of the ICF. For participants receiving sutimlimab in study TDR16218, they may continue to receive sutimlimab during screening, until at least 14 days prior to the first dose of BIVV020, as duration of the PD effect of sutimlimab is approximately 14 days. This period between the final dose of sutimlimab and the first dose of BIVV020 is known as the Transition Period.
- Enrollment in the study occurs when a participant receives the first dose of BIVV020.
- A loading dose of BIVV020 at 50 mg/kg IV will be administered on Day 1, followed by maintenance doses of 600 mg SC weekly starting on Day 8. On Day 1, participants will remain in the clinic for at least 4 hours after that start of IMP administration.
- The 600 mg SC dose will be administered as two 2 mL injections. For the first 5 weeks of maintenance therapy, the injections will be performed by the site staff, and participants will receive education on self-administration. At Week 6, the participant (or their caregiver) will perform the injection under the supervision of the site staff. Participants should be observed for 30 minutes after IMP administration for the first 6 SC administrations.
- Starting at Week 7, the injections will be performed by the participant or caregiver at home. From Weeks 7 to 12, participant will return to the clinic every other week. At clinic visits, participants (or their caregiver) will administer BIVV020 under the supervision of the study staff. Participants may request assistance with the injections from the study staff during these visits.

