7.1.4 Lack of efficacy (relapse or sustained lack of improvement) stopping criteria

The study intervention may be discontinued due to a lack of response. Determination for treatment discontinuation in this case will be made by the Investigator and Sponsor.

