9 STATISTICAL CONSIDERATIONS

9.1 SAMPLE SIZE DETERMINATION

Approximately 12 participants will be enrolled to receive the study intervention. Since there is no statistical hypothesis to be tested, the sample size is not determined statistically.

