### **4.3 PRIMARY ENDPOINT(S) ANALYSIS**

The primary endpoint is the proportions of participants who met the following criteria:

1. For naïve participants,
  - a platelet count  $\geq 50 \times 10^9/L$  OR
  - a  $\geq 20 \times 10^9/L$  increase from baseline if baseline platelet count  $< 15 \times 10^9/L$  at  $\geq 50\%$  of scheduled visits from Week 3 to Week 24.

For switchers, a platelet count  $\geq 30 \times 10^9/L$  at  $\geq 50\%$  of scheduled visits from Week 3 to Week 24.

2. No concomitant ITP therapy from Week 3 to Week 24.

Concomitant medications are defined in [Section 5.3](#). The ITP therapies will be identified by the Sanofi coding group, reviewed by medical, and defined in the programming specifications. The ITP therapies include corticosteroids, thrombopoietin receptor agonists, intravenous immunoglobulin, anti-D immunoglobulin, rituximab, fostamatinib, immunosuppressants (azathioprine, cyclosporin A, mycophenolate mofetil), cyclophosphamide, dapsone, danazol.

The response rate will be summarized for naïve participants, switchers, and total for the ITT along with the 95% exact Clopper-Pearson Confidence Interval (CI).

Platelet counts will be summarized by visit. These plots will also be provided:

- Individual platelet count profile: line plot of platelet count by visit for each participant

- Spaghetti plot platelet count by participant
- Median platelet count/change from baseline with by visit

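### Protocol 7.1.1 permits replacement of participants who stop for lack of efficacy, which ties the number enrolled to outcome and biases the primary response proportion slightly upward

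*Protocol*

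**What the plan says.** Protocol 7.1.1 opens by expecting permanent discontinuation to be uncommon: "In rare instances, it may be necessary for a participant to permanently/definitely discontinue the study intervention". It then allows replacement: "a new participant may be enrolled to replace the one who was discontinued, unless the permanent discontinuation was due to a BIVV020-related adverse reaction" or a safety concern. The list of discontinuation reasons that follows includes lack of efficacy and refers to section 7.1.4, which says "The study intervention may be discontinued due to a lack of response" and leaves the decision to the investigator and sponsor.

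On size, Protocol 9.1 says "Approximately 12 participants will be enrolled to receive the study intervention" and adds "Since there is no statistical hypothesis to be tested, the sample size is not determined statistically". Protocol 4.1 allows "up to 6 participants who have previously received and responded to sutimlimab (BIVV009) in study TDR16218", so roughly 6 to 12 of the participants would be naive.

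On analysis, the ITT is everyone dosed (Protocol Table 5) or exposed (SAP Table 2). SAP 4.3 gives the primary response rate for naive participants, switchers and "total for the ITT along with the 95% exact Clopper-Pearson Confidence Interval (CI"). Protocol 9.3.2 counts a stop before Week 3 as non-response and classifies a later stop on the available data from Week 3 to Week 24. The SAP does not mention replacement, and its disposition section (4.2) does not ask for the number replaced.

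**The concern.** Replacement makes sense when a participant leaves without giving the information the trial needs. A participant who stops for lack of efficacy has given it: he or she is dosed, is in the ITT, and has a primary outcome under Protocol 9.3.2. If such participants are replaced, a failure can add a further participant and a success cannot. The number enrolled then depends on the outcome, while the analysis treats it as fixed.

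Two things are at stake. The primary response proportion is biased upward, and enrolment can exceed about 12. Stopping for lack of response has no set criterion and the study is open-label, so both the stop and the replacement are discretionary. Without a count of replacements in the disposition summary, a reader of the results could not tell whether this had happened.

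**Working it through.** There is no power calculation to reproduce, because the plan states no hypothesis and does not derive its sample size. The check is an exact calculation of the expected response proportion under replacement.

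**Inputs**
- m, the number of naive participants not replaced for lack of efficacy: 6, or 12 for comparison. Assumed, from about 12 in total and up to 6 switchers.
- p, the true response rate: 0.5. Assumed. Protocol 2.3 reports 50% for the predecessor drug under a different response definition. Range 0.3 to 0.7.
- f, the share of non-responders who stop for lack of efficacy and are replaced: 0.10, 0.25, 0.50 and 1. Assumed; the documents give no figure.

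**Model (deliberately severe)**
Replacements can themselves be replaced, until m participants remain who were not replaced. All dosed participants stay in the denominator, as in the plan's ITT.
- Chance that a participant is not replaced: s = 1 − (1 − p)f.
- Total enrolled N is negative binomial, with E[N] = m/s.
- Each participant who is not replaced is a responder with probability p/s; replaced participants are non-responders.
- Expected ITT proportion = m × (p/s) × E[1/N].

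**Results for m = 6, p = 0.5**

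| f | s | p/s | E[1/N] | E[N] | Expected proportion | Bias (points) |
|---|---|---|---|---|---|---|
| 0.10 | 0.950 | 0.526 | 0.1595 | 6.3 | 0.504 | +0.4 |
| 0.25 | 0.875 | 0.571 | 0.1485 | 6.9 | 0.509 | +0.9 |
| 0.50 | 0.750 | 0.667 | 0.1298 | 8.0 | 0.519 | +1.9 |
| 1 | 0.500 | 1.000 | 0.0902 | 12.0 | 0.541 | +4.1 |

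For example, at f = 0.5: 6 × 0.6667 × 0.1298 = 0.519.

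**Other settings**
- m = 12, p = 0.5: +0.2, +0.5, +1.0 and +2.1 points for the same four values of f.
- m = 6, p = 0.3, f from 0.25 to 1: +0.8 to +3.7 points. With p = 0.7: +0.8 to +3.3 points.
- One replacement per stopped participant, not repeated (m = 6, p = 0.5): +1.3 points at f = 0.5 (E[N] = 7.5) and +2.0 points at f = 1 (E[N] = 9).

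**Interval.** Clopper-Pearson coverage under repeated replacement, for p from 0.3 to 0.7 and m of 6, 8 or 12, was at least 96.6%. For scale, the exact 95% interval is 11.8% to 88.2% for 3/6 and 21.1% to 78.9% for 6/12.

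**If replacement for lack of efficacy is excluded,** N no longer depends on outcome through this route, the expected proportion equals p, and this bias is zero.

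**The case against.** The strongest reply is that the rule is permissive, rarely invoked and nearly harmless. Much of this stands.

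- A reader might infer that enrolment continues until enough non-failures are found. The documents do not say so. Replacement is optional, and the only target is about 12 enrolled. The interim analysis is due when approximately 12 participants have each been treated for 15 weeks (Protocol 9.4, SAP 4.8). That gives some incentive to replace early stops, but it is not a target of non-failures. The repeated-replacement model is therefore an upper bound.
- A reader might also fear that replaced failures drop out of the denominator. That would be serious: at p = 0.5 and f = 0.5 the expected proportion would be p/s = 0.667. The ITT definitions in both documents keep them in.
- Permanent discontinuation is expected to be rare, the lack-of-response stop is discretionary, and Protocol 6.8 and 6.8.1 allow other ITP treatment after an insufficient response. Failing the primary endpoint is thus not the same as discontinuing, which points to low values of f.
- Section 7.1.4 also covers relapse. A responder over Weeks 3 to 24 may relapse later and be replaced, which offsets part of the bias. If 50% of non-responders and 25% of responders were replaced (assumed), the bias at m = 6 and p = 0.5 would be +1.0 point instead of +1.9.
- The primary proportion is not the only efficacy result. SAP 4.4 adds response at Weeks 24 and 56, the rescue-free proportion and time to response. No decision rule hangs on any of them.

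What the reply does not remove is the gap in the text. Efficacy failures may be replaced, no analytic purpose is served by it, and any resulting bias is upward unless replacement of relapsed responders offsets it.

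**Conclusion.** The point holds as a minor one. Protocol 7.1.1 permits, but does not require, replacement of participants who stop for lack of efficacy. If used, this ties the number enrolled to outcome, may carry enrolment beyond about 12, and raises the expected primary response proportion slightly.

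With 6 naive participants and a true rate of 50%, both assumed, the size is about +0.4 to +1.9 points when 10% to 50% of non-responders are replaced, and at most +4.1 points. These figures assume that only primary non-responders are replaced. The shift is small beside the width of the interval at these sample sizes, and coverage is preserved. The effect on enrolment is the more visible one: in the model, 6 naive participants become 6.3 to 8 on average over the same range of f, and 12 in the extreme case.

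**What to change.** In Protocol 7.1.1, add lack of efficacy (section 7.1.4) to the discontinuation reasons that do not permit replacement, beside BIVV020-related adverse reactions and safety concerns. In SAP 4.2, add the number of replaced participants, with reasons, to the disposition summary. No change to the ITT is needed.

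The cost is one clause in a protocol amendment and one line in a table. The downside is slightly fewer participants with long exposure, since those who stop for lack of efficacy would not be replaced.
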